10.1.11 Prior Medications

The investigator or qualified designee will review prior medication use, including any protocol-specified washout requirement, and record prior medication taken by the participant within 35 days before starting the trial. Treatment for the disease for which the participant has enrolled in this study will be recorded separately and not listed as a prior medication.

10.1.12 Concomitant Medications

The investigator or qualified designee will record medication, if any, related to reportable SAEs which should be recorded as defined on the SAE CRF.

10.1.13 Numerical Pain Rating Score

Numerical Pain Rating score (refer to Appendix 2) will be completed by the patient at the time points specified in the Schedule of Events (Section 2).

10.1.14 Tumour Imaging and Assessment of Disease

Imaging will be performed as per below:

- All pre-registration/screening investigations (CT Scan and WBBS) should be completed within 35 days prior to study registration.
- Clinical and radiological tumour assessments (post study registration) will be performed by CT scan or MRI (Chest, Abdo, Pelvis, and Brain if clinically indicated) reported with RECIST 1.1 (if possible) unless evidence of progression earlier or clinically inappropriate. WBBS will be performed at 3 and 6 months post SABR treatment in patients with bone disease detected at baseline, and/or if clinically indicated at any of the 3 monthly follow-up visits. Follow-up visits will continue until the last evaluable patient completes 12 months of follow-up.

Disease progression, as per RECIST 1.1, should be confirmed with repeat imaging 4 to 6 weeks later by the same imaging modality or by biopsy. If PET-CT scan has been done this can be used for confirmation of disease progression provided the CT component of the PET-CT scan is of adequate resolution. Complete response includes disappearance of the target tumor radiographically or metabolically (standardized uptake value = 0 when the pre-treatment PET, if done, was metabolically active). Efficacy will be evaluated by time to local progression as well as failures in other sites.

10.1.15 Laboratory Procedures/Assessments

Laboratory assessments will be performed as specified in the Schedule of Events.

Laboratory tests for screening or entry into the Second Course Phase should be performed within 10 days prior to the first dose of treatment. After Cycle 1, pre-dose laboratory procedures can be conducted up to 72 hours prior to dosing. Results must be reviewed by the investigator or qualified designee and found to be acceptable prior to each dose of trial treatment.

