2 SCHEDULE OF EVENTS

Table 1: Schedule of Events

Trial Period:	Screening Phase	Radiotherapy	Treatment Cycles		Safety Follow-up	Follow-up ¹⁷	Progression (Upon first progression)
Treatment Cycle/Title:	Screening	SABR±CRT ³	Day 1 Cycle 1	Day 1 Cycle 2-8			
Scheduling Window (Days):	-35 to -1	Commence within 4 weeks of registration ³	5 days post SABR ± 3 days	21 days post previous cycle Day 1 ± 3 days	30 days from date of last dose of pembrolizumab ± 3 days	3 months from SABR ± 14 days	
Clinical/Administrative Assessments							
Informed Consent	X						
Inclusion/Exclusion Criteria	X						
Demographics and Medical History	X						
Disease Specific Medical History	X						
SINS score for Spinal Targets	X						
Full Physical Examination	X		X	X			
Directed physical Examination						X	
Vital Signs ¹ and Body Measurements	X		X	X		X	
ECOG Performance Status	X		X	X		X	
Review Adverse Events ²	X		X	X	X	X	X
Radiotherapy planning	X						
Trial Treatment Administration – SABR ³		X					
Trial Treatment Administration – Pembrolizumab ⁴			X	X			See section 10.6
Review Prior/Concomitant Medications	X		X	X			
Numerical Pain Rating Score		X	X	X		X	
New Anti-Cancer Therapy Status / Second phase pembrolizumab					X	X	X
Survival Status ¹⁸						X	
Laboratory Procedures/Assessments: analysis performed by LOCAL laboratory							

Trial Period:	Screening Phase	Radiotherapy	Treatment Cycles		Safety Follow-up	Follow-up ¹⁷	Progression (Upon first progression)
Treatment Cycle/Title:	Screening	SABR±CRT ³	Day 1 Cycle 1	Day 1 Cycle 2-8			
Scheduling Window (Days):	-35 to -1	Commence within 4 weeks of registration ³	5 days post SABR ± 3 days	21 days post previous cycle Day 1 ± 3 days	30 days from date of last dose of pembrolizumab ± 3 days	3 months from SABR ± 14 days	
Pregnancy Test ⁵ – Urine or Serum β-HCG	X		X	X			
Haematology ⁶	X		X	X		As clinically indicated	
Chemistry ^{7,8}	X		X	X			
T3, FT4 and TSH ⁹	X		X	X			
PT/INR and aPTT ¹⁰	X						
HIV, Hepatitis B and C ¹¹	X						
Tumour Evaluation							
Tumour assessment by CT scan or MRI ¹² (Chest, Abdo, Pelvis) reported as per RECIST 1.1	X				X (Every 3 months from SABR)		
CT scan (Brain) (if clinically indicated) ¹²	X			X (Cycle 4 & 8 only)		As clinically indicated	
Whole body bone scan (if clinically indicated) ¹²	X			X (Cycle 4 & 8 only)		As clinically indicated	
Metastatic FFPE Biopsy ¹³	X					X (month 9 only)	X
Primary Surgery FFPE sample ¹⁴	X						
Blood Serum Sample		X	X	X		X (9, 12 and 24 months)	X

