Whole Blood Sample ^{15,16}		X	X	X		X (9, 12 and 24 months)	X

Clinical/Administrative Assessments

- Vital signs include blood pressure, heart rate, respiratory rate and temperature. Height will be measured at screening only.
- Baseline abnormalities (using CTCAE v4.03) must be recorded from signature of informed consent to prior to start of treatment. Adverse events (using CTCAE v4.03) are then required to be assessed on day 1 of every pembrolizumab cycle and at 30 days following last pembrolizumab treatment. SABR related adverse events will be collected at every subsequent follow-up visit until 2 years after completion of SABR.

3. Conventional hypofractionated radiotherapy of **30-36Gy** may be delivered to individual lesion(s) if SABR is determined to be not technically or safely possible to deliver. If CRT is required it must be completed prior to SABR administration. **At least one lesion must receive SABR.**

4. Pembrolizumab should be administered at 5 days (+/- 3 days) of the last SABR treatment for a total of 8 cycles.

Laboratory Procedures/Assessments – All diagnostic laboratory tests should be performed within 10 days of study registration (to determine eligibility), and also within 3 days prior to every cycle of pembrolizumab (unless indicated otherwise below)

5. Urine or serum pregnancy test for patient of childbearing potential should be performed within 7 days of study registration and also 72 hours within first dose of pembrolizumab. If the urine test is positive or cannot be confirmed as negative, a serum pregnancy test will be required.

6. Haematology: Haematocrit, haemoglobin, platelet count, white blood cell count (total and differential), red blood cell count, absolute neutrophil count and absolute lymphocyte count.

7. Chemistry: Carbon dioxide (if considered standard of care only), uric acid, calcium chloride, glucose, phosphorus, potassium, sodium, magnesium, total protein.

8. Liver Function Tests: Albumin, Alkaline Phosphatase (ALP), Alanine Aminotransferase (ALT), Aspartate Aminotransferase (AST), Lactate Dehydrogenase (LDH), Gamma-Glutamyl Transferase (GGT, total bilirubin and direct bilirubin if total bilirubin is elevated above the ULN), Kidney Function Tests: Urea, creatinine.

9. Thyroid Function: T3, T4 and TSH.

10. Coagulation Profile: PT (INR), aPTT. These need only be done if there is clinical concern regarding patient anticoagulation.

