8.3 Participant Inclusion Criteria

In order to be eligible for participation in this trial, the participant must:

1. Has provided written informed consent for the trial.
2. Be ≥ 18 years of age on day of signing informed consent.
3. Have oligometastases (1-5 metastases), and measurable disease based on RECIST 1.1.
4. Participants must have a histologically or cytologically confirmed metastatic renal cell carcinoma. Oligometastatic lesions do not need to be biopsied but they must be clinically consistent to represent metastatic disease.

5. Patient can either be treatment naïve or have previously received up to 2 lines of systemic treatment (eg. Pazopanib or Sunitinib). If patient has received prior systemic therapy, the total number of metastases that have not been treated with definitive local therapies should not number more than 5.
6. Must have had surgical consideration for metastasectomy and thought appropriate for SABR due to medical inoperability, technical factors or patient declining surgery.
7. Must have at least one metastasis for which SABR is technically deliverable.
8. Be willing to provide archival tissue from a previously biopsied or excised primary or metastatic RCC lesion (if available). If safe to do so, a request for newly obtained specimen (obtained up to 5 weeks prior to trial registration) will be made, however participation for this biopsy is entirely optional.
9. Have a performance status of 0-2 on the ECOG Performance Scale (Appendix 1)
10. Demonstrate adequate organ function as defined in Table 3, all screening labs should be performed within 10 days of registration.

Table 3: Adequate Organ Function Laboratory Values

System	Laboratory Value
Haematological	
Absolute neutrophil count (ANC)	$\geq 1.5 \times 10^9/L$
Platelets	$\geq 100 \times 10^9/L$
Haemoglobin	$\geq 90 \text{ g/L}$ or $\geq 5.6 \text{ mmol/L}$ without transfusion or EPO dependency (within 7 days of assessment)
Renal	
Serum creatinine OR Measured or calculated ^a creatinine clearance (GFR can also be used in place of creatinine or CrCl)	$\leq 1.5 \times$ upper limit of normal (ULN) OR $\geq 30 \text{ mL/min}$ for participant with creatinine levels $> 1.5 \times$ institutional ULN
Hepatic	
Serum total bilirubin	$\leq 1.5 \times$ ULN OR Direct bilirubin \leq ULN for participants with total bilirubin levels $> 1.5 \times$ ULN
AST (SGOT) and ALT (SGPT)	$\leq 2.5 \times$ ULN OR $\leq 5 \times$ ULN for participants with liver metastases

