Albumin	$\geq 2.5 \text{ mg/dL}$
Coagulation	
International Normalized Ratio (INR) or Prothrombin Time (PT)	$\leq 1.5 \times$ ULN unless participant is receiving anticoagulant therapy as long as PT or PTT is within therapeutic range of intended use of anticoagulants
Activated Partial Thromboplastin Time (aPTT)	$\leq 1.5 \times$ ULN unless participant is receiving anticoagulant therapy as long as PT or PTT is within therapeutic range of intended use of anticoagulants
^a Creatinine clearance should be calculated per institutional standard.	

11. Life expectancy > 12 months.
12. Be willing and able to comply with all study requirements, including treatment, attending assessments and follow-up.
13. Female participant of childbearing potential should have a negative urine or serum pregnancy within 7 days prior trial registration. If the urine test is positive or cannot be confirmed as negative, a serum pregnancy test will be required.
14. Female participants of childbearing potential should be willing to use 2 methods of birth control or be surgically sterile, or abstain from heterosexual activity for the course of the study through 120 days after the last dose of study medication (see Section 9.4.2: Contraception). Participants of childbearing potential are those who have not been surgically sterilized or have not been free from menses for > 1 year.
15. Male participants should agree to use an adequate method of contraception starting with the first dose of study therapy through 120 days after the last dose of study therapy.

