9.1.2 Treatment Schedule

Radiation therapy should commence within 4 weeks of patient registration on the study. A single dose of 20 Gy should be prescribed, although a single 18Gy fraction can be used as an alternative for a centrally located lung lesion or a spinal lesion with a SINS score of ≥ 7 after review at SABR chart round. Typically a single fraction of 20Gy should be prescribed for spinal vertebral lesions, however, for those with a SINS score of ≥ 7 after review at SABR chart round, a single 18Gy fraction is preferred.

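### No repeat pregnancy test is required before radiotherapy, so the screening test can be 35 days old at first irradiation; the lab window in 10.1.15 should also be aligned with the Schedule

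*Combined protocol and SAP*

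**What the plan says.** **Pregnancy test.** Inclusion criterion 13 (section 8.3) reads: "Female participant of childbearing potential should have a negative urine or serum pregnancy within 7 days prior trial registration". Note 5 of the Schedule of Events (section 2) says the test "should be performed within 7 days of study registration and also 72 hours within first dose of pembrolizumab". In Table 1 the pregnancy-test row is marked at screening and on Day 1 of the pembrolizumab cycles, but not in the radiotherapy column.

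**Treatment timing.** Section 9.1.2: "Radiation therapy should commence within 4 weeks of patient registration on the study". Schedule note 3 requires any conventional radiotherapy (CRT) to be finished before SABR. Section 9.1.13 allows the SABR sessions to span 21 calendar days. Section 9.1.18 starts pembrolizumab 5 days, plus or minus 3, after the last SABR.

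**Other laboratory tests.** The Schedule says: "All diagnostic laboratory tests should be performed within 10 days of study registration (to determine eligibility), and also within 3 days prior to every cycle". Inclusion criterion 10 agrees: "Demonstrate adequate organ function as defined in Table 3, all screening labs should be performed within 10 days of registration". Section 10.1.15 counts from a different date: "Laboratory tests for screening or entry into the Second Course Phase should be performed within 10 days prior to the first dose of treatment". The same section opens with: "Laboratory assessments will be performed as specified in the Schedule of Events".

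**The concern.** The protocol asks for a recent negative pregnancy test before the first pembrolizumab dose (Schedule note 5) and again before retreatment (section 10.6), each time within 72 hours. It sets no such rule before radiotherapy, which comes first and includes a single ablative fraction of 18 to 20 Gy. Exclusion criterion 17 bars pregnant women, but until radiotherapy it rests on a test tied to registration. A pregnancy that begins between registration and irradiation need not be detected until the pre-pembrolizumab test, which normally follows SABR. What is at stake is the safety of a small number of women, not an estimate.

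The differing lab windows are a smaller matter. Section 10.1.15 counts back from treatment, while the Schedule and criterion 10 count from registration. The two dates can be four weeks apart, so a site or monitor could be unsure which window applies.

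**Working it through.** The plan states no figure to reproduce. The check is day-counting on the stated windows.

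**Inputs**
- Screening pregnancy test: up to 7 days before registration (criterion 13, Schedule note 5).
- Start of radiotherapy: up to 28 days after registration (9.1.2).
- SABR sessions: within 21 calendar days, so the last is at most 20 days after the first (9.1.13).
- CRT, where used: up to 12 fractions (9.1.3). Five weekday fractions a week is my assumption.
- First pembrolizumab dose: 2 to 8 days after the last SABR (9.1.18).
- Second pregnancy test: 0 to 3 days before that dose (Schedule note 5).

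**Oldest permitted screening test**
- At first irradiation: 7 + 28 = **35 days**.
- At SABR after 12 CRT fractions: a Monday start puts the last fraction 15 days after the first and SABR on day 16 at the earliest, so 35 + 16 = **51 days**. A Friday start puts the last fraction on day 17 and SABR on day 18, so 35 + 18 = **53 days**.
- At the last SABR when sessions are spread out: 35 + 20 = **55 days** (56 if the 21 days are counted as elapsed days).

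I have not added the CRT and SABR spreads together, because section 9.1 can be read as putting all lesions inside one 21-day window.

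**When the next test falls, relative to the last SABR**
- At the planned 5-day gap: 5 − 3 = 2 to 5 − 0 = 5 days after.
- Across the full window: 2 − 3 = −1 to 8 − 0 = 8, that is, from 1 day before to 8 days after.
- Of the 7 × 4 = 28 whole-day combinations of gap (2 to 8 days) and test day (0 to 3 days earlier), 3 fall on or before the day of the last SABR: a gap of 2 with the test 2 or 3 days earlier, and a gap of 3 with the test 3 days earlier. These are permitted but not required.
- Longest interval between the two tests without CRT: 7 + 28 + 20 + 8 = 63 days.

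**Does 10.1.15 close the gap?** If its first dose means SABR (Table 1 has a row headed "Trial Treatment Administration – SABR") and the pregnancy test counts as a screening lab, the test would be at most 10 days old at SABR. But note 5 gives the pregnancy test its own timing, and 10.1.15 sends the reader to the Schedule. If first dose means pembrolizumab, 10.1.15 says nothing about radiotherapy. It cannot be relied on to close the gap.

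**Other labs.** Under the Schedule the oldest screening panel at first radiotherapy is 10 + 28 = 38 days. Under 10.1.15, read as counting back from radiotherapy, it is 10 days. One sample taken at or before registration can meet both windows only if radiotherapy starts by day 10.

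**Effect of the fix.** A test within 72 hours before the first fraction cuts 35 days to 3. That test alone would be 3 + 16 = 19 days old at SABR after CRT (Monday start), or 3 + 20 = 23 days old at the last of the spread sessions. A repeat is therefore needed when SABR falls on a later date.

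**The case against.** The strongest reply is that safeguards already exist. A negative test is mandatory before registration. Inclusion criterion 14 requires two contraceptive methods, surgical sterility or abstinence, and section 9.4.2 starts birth control at the first visit. Section 10.1.15 also requires results to be reviewed and found acceptable before each dose of trial treatment. All of this stands and lowers the risk. None of it detects a pregnancy that begins after the screening test: contraception is not a test, and reviewing an existing result is not a new sample. It would be wrong to infer that no pregnancy test precedes radiotherapy; the criterion 13 test does, but it need not be repeated.

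On the other labs, a reader might infer that anyone starting radiotherapy after day 10 is a protocol deviation. The documents do not support that. Section 10.1.15 defers to the Schedule, criterion 10 agrees with the Schedule, and the next sentence of 10.1.15 speaks of Cycle 1, which points to pembrolizumab. Nothing forbids a second sample that would satisfy both windows.

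A reader might also infer that Table 6 note a, which stops the drug on a rise in AST or ALT from baseline, lacks a usable baseline. That note sits in the pembrolizumab dose-modification section, and the Schedule requires a sample within 3 days before Cycle 1. At most a detail is missing, and moving the baseline before radiotherapy could attribute a SABR-related rise to the drug.

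**Conclusion.** The point holds as a minor safety gap in the schedule of tests. A woman of childbearing potential can be irradiated on a pregnancy test up to 35 days old, and about 51 to 55 days old at SABR in the longer sequences. The next required test normally falls after SABR. The 35 days follow directly from the stated windows. The 51 and 53 days also assume five weekday CRT fractions a week.

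The plan does not say how many women of childbearing potential are expected. I assume 0 to 3 of the 30 evaluable patients, and at the lower end nobody is affected.

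The difference between 10.1.15 and the Schedule is an inconsistency of wording. A reader might infer from it, or from the varied terms for the start of treatment, that the primary safety rate is affected. The documents do not support this: section 10.8.1 records all adverse events from consent, and laboratory values count only if abnormal and judged clinically significant. No statistical figure in the plan changes.

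**What to change.** 1. **Schedule note 5 and Table 1.** For women of childbearing potential, require a negative urine or serum pregnancy test within 72 hours before the first radiotherapy fraction, whether CRT or SABR. Repeat it before SABR if SABR falls on a later date. Mark the radiotherapy column of the pregnancy-test row to match.
2. **Section 10.1.15 (housekeeping).** State that eligibility labs are taken within 10 days before registration, as in the Schedule, and that labs for the Second Course Phase are taken within 10 days before the first dose of that course.

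The cost is an edit in each of these places and usually one or two urine tests for a few women, with more only if SABR is split over several dates. The second edit removes the ambiguity but leaves the 38-day maximum age of the general labs at first radiotherapy as it is. I do not ask for an extra blood panel. No analysis changes.

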10.1.16 Subsequent Anti-Cancer Therapy Status

The investigator or qualified designee will review all new anti-neoplastic therapy initiated after the last dose of trial treatment. If a participant initiates a new anti-cancer therapy within 30 days after the last dose of trial treatment, the 30 day Safety Follow-up visit must occur before the first dose of the new therapy. Once new anti-cancer therapy has been initiated the participant will move into survival follow-up.

10.1.17 Continuing Pembrolizumab beyond Radiological Progression

There are patients who experience progression prior to response to pembrolizumab. Hence, radiological progression should be confirmed with follow-up imaging 4-6 weeks later. Pembrolizumab can be continued if there is evidence of benefit by the investigator, if there are no signs or symptoms indicating unequivocal disease progression, no decline in ECOG performance status attributed to disease progression and no growth of the tumour in critical sites. If radiological progression is still documented pembrolizumab can still be continued until there is unequivocal symptomatic deterioration attributed to disease progression that requires initiation of new systemic or local therapy.

10.2 Visit Requirements

Visit requirements are outlined in The Schedule of Events (Section 2). Specific procedure-related details are provided above in Section 10: Trial Procedures.

10.3 Safety Follow-Up Visit

The mandatory Safety Follow-Up Visit should be conducted 30 days \pm 3 days after the last dose of trial treatment or before the initiation of a new anti-cancer treatment, whichever comes first. All AEs that occur prior to the Safety Follow-Up Visit should be recorded. Participants with an AE of Grade > 1 will be followed until the resolution of the AE to Grade 0-1 or until the beginning of a new anti-neoplastic therapy, whichever occurs first. SAEs that occur within 90 days of the end of treatment or before initiation of a new anti-cancer treatment should also be followed and recorded.

